5.2.4 Sequential Dosing Scheme

The study dosing will initiate in Dosing Group I (the lowest dose), and continue to Dosing Group II after completion of enrollment. Each dosing group will enroll sequentially following completed enrollment of the previous dosing group. After all active subjects within each dosing group have completed 72 hours, the SRC will review the safety and tolerability of this dose.

If there appears to be intolerability with a given dose or operational challenges administering a dose, the remaining subjects may have the dose decreased to a previously administered dose, after consultation with the SRC.

Further details on the dosing for each dosing group are provided in Section 5.2.2.

5.2.5 Repeat Dosing

In order to ensure the safety of repeat dosing, specifically in regards to AEs and electrolyte changes (such as sodium and potassium levels), and to ensure subjects with a demonstrated need receive treatment, 1 repeat dose will be allowed for all dosing groups. The repeat dose will consist of repeating the same dose and will occur between 2 and 24 hours after the initial dose, if the repeat dosing criterion is met. The repeat dosing criterion is defined as at least 2 hours, but no more than 24 hours, after dosing and the subject must require a sustained need for supplemental oxygen at or above the qualifying FiO_2 level for study entry (ie, 0.25) for at least 30 minutes to maintain SpO_2 of 88% to 95%.

As with the initial dose, the IWRS will be used to receive the study drug assignments, and all other procedures that were performed for the initial dose will be followed for the administration of the repeat dose.

[figure not shown]
If, in the opinion of the PI, repeat dosing would compromise the safety of the subject, repeat dosing will not occur.

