7.1.7 Serum Electrolytes

Serum electrolytes (Na⁺, Cl⁻, K⁺, and Total CO₂) will be measured 24 hours from the time of randomization (± 6 hours).

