- ⁸ Serum electrolytes are to be evaluated 24 hours from randomization (± 6 hours) (Section 7.1.7)
- ⁹ Gastric liquid volume will be assessed 30 minutes (± 15 minutes) following completion of lucinactant for inhalation administration. Enteral feedings are to be held during and ≥ 1 hour following completion of lucinactant for inhalation administration (Section 7.1.9).
- ¹⁰ Peri-dosing events are defined as any adverse event with an onset time ≤ 2 hours from the time of initiating administration of lucinactant for inhalation

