2.2.2 Repeat Dosing

In order to ensure the safety of repeat dosing, specifically in regards to AEs and electrolyte changes (such as sodium and potassium levels), and to ensure subjects with a demonstrated need receive treatment, 1 repeat dose will be allowed for all dosing groups. The repeat dose will

consist of repeating the same dose, and will occur between 2 and 24 hours after the initial dose, if the repeat dosing criterion is met. The repeat dosing criterion is defined as: at least 2 hours, but no more than 24 hours, post dosing and a FiO_2 level of at least 0.35.

If, in the opinion of the PI, repeat dosing would compromise the safety of the subject, repeat dosing will not occur.

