6.5.3 Electrolytes

Sodium, chloride, potassium, and total carbon dioxide (CO₂) will be summarized at 24 hours post randomization as continuous variables. Clinically significant values will also be recorded as AEs.

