- 7.2 Clinical Assessments – Serum Electrolytes – Observed Values – Safety Population
- 7.3 Clinical Assessments – Gastric Liquid Volume and Defecation – Safety Population
- 7.4.1 Clinical Assessments – Physical Examination – Safety Population
- 7.4.2 Clinical Assessments – Physical Examination: Shift Table – Safety Population
- 7.5.1 Clinical Assessments – Respiratory Parameters – FiO₂ – Safety Population
- 7.5.2 Clinical Assessments – Respiratory Parameters – SpO₂ – Safety Population
- 7.5.3 Clinical Assessments – Respiratory Parameters – PCO₂ – Safety Population
- 7.6.1 Clinical Assessments – Respiratory Support in the Delivery Room and Mechanical Ventilation – Safety Population
- 7.6.2 Clinical Assessments – Supplemental Oxygen – Safety Population
- 7.7 Clinical Assessments – nCPAP Settings – Safety Population
- 7.8 Clinical Assessments – Complications of Prematurity – Safety Population

Listing Title

- 1.1 Protocol Violations/Deviations
- 2.1 All-Cause Mortality
- 2.2 Serious Adverse Events
- 3.1 Early Termination of Aerosol Treatment
- 3.1 Pre-Study/Concomitant Medications
- 4.1 Mechanical Ventilation Information by Subject
- 4.2 Supplemental Oxygen Information by Subject

Figure Title

- 1.1.1 FiO₂ Observed Values by Treatment Group
- 1.1.2 FiO₂ Change from Baseline Values by Treatment Group
- 1.2.1 SpO₂ Observed Values by Treatment Group
- 1.2.2 SpO₂ Change from Baseline Values by Treatment Group
- 1.3.1 PCO₂ Observed Values by Treatment Group
- 1.3.2 PCO₂ Change from Baseline Values by Treatment Group
- 2.1 FiO₂ Change from Baseline Values by All Active and Control
- 2.2 SpO₂ Change from Baseline Values by All Active and Control
- 2.3 PCO₂ Change from Baseline Values by All Active and Control

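### Electrolyte safety is one stated reason for repeat dosing, but the only scheduled electrolyte sample can precede the repeat dose, and the planned outputs do not separate one-dose from two-dose values

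*Protocol*

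**What the plan says.** Protocol 5.2.5 opens with the purpose of repeat dosing: "In order to ensure the safety of repeat dosing, specifically in regards to AEs and electrolyte changes (such as sodium and potassium levels". The same sentence adds a second purpose: "to ensure subjects with a demonstrated need receive treatment, 1 repeat dose will be allowed for all dosing groups". SAP 2.2.2 repeats the electrolyte wording: "specifically in regards to AEs and electrolyte changes (such as sodium and potassium levels".

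Serum electrolytes (sodium, chloride, potassium and total CO2) appear once in the schedule. Protocol 7.1.7 says they "will be measured 24 hours from the time of randomization", with a window of ±6 h. The footnotes to Protocol Appendix 2 and the SAP 2.2.4 schedule say the same. The screening list in Protocol 8.1 contains no electrolytes, and no sample is linked to the first or the repeat dose.

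In the analysis, SAP 6.5.3 says the values "will be summarized at 24 hours post randomization as continuous variables". Table 7.2 is titled "Clinical Assessments – Serum Electrolytes – Observed Values – Safety Population", whereas the titles of the vital-sign tables (7.1.1 to 7.1.3) also include change from baseline. SAP 9.2 states that summary tables use nominal rather than actual times. SAP 4.5 plans no subgroup summaries, SAP 3.3.2 and 6.3 only count repeat doses, and the SAP's list of listings has none for electrolytes.

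**The concern.** The plan names electrolyte change as something repeat dosing must be safe on, but fixes the only electrolyte measurement by time from randomization. Some repeat-dosed infants may therefore have sodium and potassium measured after one dose only. Where the sample does follow the repeat, the lag is uncontrolled. With no scheduled pre-dose value, within-infant change cannot be calculated from planned data.

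The outputs as planned would not reveal which values are which. Protocol 6.1 has the SRC review summary tables of all safety endpoints, and its options include moving to the next dose level with its own potential repeat dose. Protocol 2.2.3 itself raises the possibility of an effect on serum electrolytes. The risk is that values drawn before a repeat are read as evidence about the repeat.

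**Working it through.** The plan states no figure on this point, so the check is timeline arithmetic. All times are hours after randomization.

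**Inputs**
- Start of first dose: within 2 h (Protocol 5.2.1). The earliest practical start is about 0.5 h, because PCO2 monitoring begins after randomization and at least 30 min before delivery (Protocol 7.1.5).
- Dose duration d: 0.5, 0.75, 1.0 or 1.5 h for Groups I to IV (Protocol 5.2.2).
- Repeat window: 2 to 24 h after completion of the first dose (Protocol summary and SAP executive summary). Protocol 5.2.5 counts from the initial dose without saying whether from its start or its end.
- Sample window: 24 ± 6 = 18 to 30 h.

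**Latest permitted repeat**
- Counted from completion: latest start = 2 + d + 24, and latest end = latest start + d.
- Counted from initiation: latest start = 2 + 24 = 26.0 h in every group.

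Either way, the latest start lies inside the 18 to 30 h sample window.

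**Share of repeats still to start when the sample is drawn (illustration)**

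Assume the first dose starts uniformly between 0.5 and 2 h (mean 1.25 h) and the repeat starts uniformly 2 to 24 h after completion (a 22 h window). The window closes on average at C = 1.25 + d + 24. For a sample at time t, the share is (C − t)/22.

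| Group | Latest start | Latest end | C | Sample at 24 h | Sample at 18 h |
|---|---|---|---|---|---|
| I | 26.5 | 27.0 | 25.75 | 1.75/22 = 8.0% | 7.75/22 = 35.2% |
| II | 26.75 | 27.5 | 26.0 | 2.0/22 = 9.1% | 8.0/22 = 36.4% |
| III | 27.0 | 28.0 | 26.25 | 2.25/22 = 10.2% | 8.25/22 = 37.5% |
| IV | 27.5 | 29.0 | 26.75 | 2.75/22 = 12.5% | 8.75/22 = 39.8% |

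**Sample times uniform over 18 to 30 h**

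The share is the mean of (window close − 18)² divided by 2 × 12 × 22 = 528. The variance of the close time is 1.5²/12 = 0.1875.
- Group I: (7.75² + 0.1875)/528 = 60.25/528 = 11.4%
- Group IV: (8.75² + 0.1875)/528 = 76.75/528 = 14.5%

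A simulation of 10⁶ draws gave 11.4% and 14.6%. Counting samples drawn before the end of the repeat, which includes those drawn during it, gave 12.9% and 19.9%.

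**In infants**

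If all 8 active infants in Group IV had a repeat, 8 × 0.125 = 1.0 would be expected to have a pre-repeat value with samples at 24 h, and 8 × 0.398 = 3.2 with samples at 18 h.

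**Lag when the sample does follow**

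The earliest Group I repeat starts at 0.5 + 0.5 + 2 = 3.0 h and ends at 3.5 h. A sample at 30 h then comes 26.5 h later. Permitted lags therefore run from near zero to 26.5 h.

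**The case against.** The other side has real points.

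- **Purpose.** Electrolyte safety is not the only reason for repeat dosing. Need is named in the same sentence, and the verb is ensure, not demonstrate. This stands, but it does not remove the electrolyte purpose.
- **Early repeats.** The protocol's repeat threshold is the entry FiO2 level of 0.25, and the window opens 2 h after the first dose, so infants with persisting need could qualify early, before any sample is due. This stands, and the uniform assumption may overstate the shares. SAP 2.2.2 gives a different FiO2 threshold (0.35), which has to be reconciled separately.
- **Adverse events.** SAP 6.5.3 has clinically significant values recorded as AEs, and the SRC reviews all AEs. This covers abnormal values that someone happens to draw. It is not systematic measurement after the repeat.
- **Recorded times.** SAP 9.2 requires clock times for timed events, and Protocol 8.2 records aerosol start and completion. The order of sample and repeat can therefore be derived, which makes the remedy cheap, but no planned output uses it.
- **Controls.** Sampling both arms at the same nominal time allows a comparison of levels. It gives neither within-infant change nor a repeat-dose effect.
- **Procedures at the repeat.** Protocol 5.2.5 applies first-dose procedures to the repeat, but no electrolyte sample belongs to the first dose, so none is added.

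A reader might go further in three ways. One is to infer that most repeat-dosed infants would be sampled too early. That needs late repeats and 18 h samples together: with all repeats 12 to 24 h after completion and all samples at 18 h, the shares are 7.75/12 = 65% to 8.75/12 = 73%. Nothing in the documents suggests that pattern. Another is to infer that the trial will report no electrolyte effect of repeat dosing, but no such analysis is planned. A third is to infer that no pre-dose values will exist. The documents show only that none is scheduled, and routine-care results may be available.

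**Conclusion.** The point holds as a mismatch between a stated purpose and the measurement and reporting planned for it. A compliant sample can precede a permitted repeat under either reading of the 24 h limit, no pre-dose value is scheduled, and values after one and two doses would be mixed in the planned summary.

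The size is moderate. Under uniform timing, roughly one repeat-dosed infant in twelve (Group I) to one in eight (Group IV) is sampled before the repeat starts at the nominal 24 h, and more than a third at 18 h. These shares rest on assumed dose and sample times and would fall if repeats are given early. For many repeat-dosed infants the sample will follow the repeat and be informative. That Table 7.2 will not mark the two kinds of value is inferred from its title and the SAP text, since no table shell is shown. The change is worth making because groups are small and the information needed is largely recorded already.

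**What to change.** Keep the 24 h sample for all infants. Moving it for repeat-dosed infants would not work: at 18 to 24 h the site cannot know whether a repeat will follow, and timing would then depend on a post-randomization event in the active arm only, which breaks the common time point with controls.

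1. **SAP 6.5.3 and Table 7.2.** Classify each active-arm value by actual sample time as no repeat given, or drawn before, during or after the repeat. Show values after one dose and after two doses separately.
2. **Listing.** Add an electrolyte listing of sample time against dose start and end times. Include it and the split table in the SRC package.
3. **eCRF.** Record any clinically obtained electrolyte result closest before randomization, and the first one after completion of a repeat dose within the 48 h Primary Observation Period. Add no blood draw. Show change where both values exist.
4. **Interpretation.** State in the SAP that conclusions on repeat dosing and electrolytes rest only on values drawn after the repeat.
5. **Wording.** Reconcile the passages that count the repeat window from completion with those that count it from the initial dose.

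The cost is a few extra eCRF fields and SAP wording. Cells will be small, and clinically obtained values will not be available for every infant, so the change-from-baseline display will be incomplete and should say how many infants contribute.

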5.3 Aerosurf Delivery System

The ADS creates and controls aerosolized surfactant (lucinactant for inhalation) through 2 components, the ACU (Section 5.3.1) and the disposable ADP (Section 5.3.2). At the patient interface, two external flow sources are combined: humidified air from the CPAP system and carrier gas flow from the ADS (Figure 5.3-1). The entire ADS is a device designed for bedside use, and is mounted on a wheeled cart for easy transport.

A complete qualitative risk assessment has been completed to identify and mitigate potential safety risks associated with use of the ADS.

Figure 5.3-1. Aerosol Delivery System

The ADS produces the aerosolized form of lucinactant through heat and pressure created within the CAG located within the heater assembly. The ADP is in-line to the ACU, and jointly these two components produce, control and monitor the key elements necessary for the production of aerosolized surfactant (lucinactant for inhalation). A summary of the key functions each of the

ADS components (ACU and ADP) contributes to the aerosolization of lucinactant is provided in [Table 5.3-1](#).

Table 5.3-1 Key Function of Aerosurf Control Unit and Aerosurf Delivery Pack

Key Component	Aerosurf Control Unit	Aerosurf Delivery Pack
Carrier Gas ¹	N/A	Contains the carrier gas tube assembly that is connected to an external gas source ¹ .
Heater	Measures and controls the heater, which enables aerosol generation	Contains the heater assembly, placed in line with the Aerosol Control Unit to heat lucinactant for inhalation.
Lucinactant	Contains a chamber with a locking door mechanism to accept the filled syringe; prevents access to syringe chamber after aerosolization is started.	Includes a 60 ml syringe, which is filled to the maximum volume with lucinactant for inhalation.

¹ Carrier gas is an external flow source of oxygen and room air blends, at percentages that are in accordance with the study protocol, subject safety, and best medical judgment as directed by the PI.

5.3.1 Aerosurf Control Unit

The ACU contains a syringe pump mechanism integrated with control electronics and a temperature probe. The control electronics consists of embedded hardware and software with a touch screen interface that provides sequential instruction for (1) ADS set-up, (2) system operation, (3) safety interventions, and (4) temperature control. A cart is provided for use with the ACU. Materials and dimensions for the ACU are consistent with similar equipment used in critical care environments.

5.3.2 Aerosurf Delivery Pack

The ADP is a single-use, disposable pack containing a 60 ml syringe, the tube assembly, and the heater assembly. A summary of the ADP functions are provided in [Table 5.3-1](#).

5.3.2.1 ADP Set-up

Instructions for the proper set-up and connections of ADP components are provided in the ADS Operator’s Manual. Depending upon the dose, 1 or 2 ADPs will be required for each treatment.

The syringe is filled to maximum volume with the lucinactant suspension and placed in the syringe sleeve located in the ACU. To ensure full aerosol delivery, and proper functionality of

the device, it is imperative that the syringe is filled to the maximum volume and all air bubbles are removed before placement into the device.

5.3.2.2 ADP Post Delivery Procedures

The ADP must be disengaged from the ADS and returned to Discovery after completion of aerosol delivery (as indicated on the ACU screen). All fluid should be removed from the aerosol tubing and fluid traps in accordance with local institutional practices before shipping.

Instructions on proper removal of the ADP from the ADS are provided in the ADS Operator's Manual.

Study ADPs are required to be returned to 1 of 3 return facilities in accordance to the following categories.

1. Unused ADPs are shipped to Battelle at the time of site closure or at the request of Discovery (clinical site monitors will provide additional information to study sites on associated shipping procedures and addresses);
2. Used ADPs that are not associated device errors are picked-up by a specified vendor for destruction;
3. ADPs associated with device errors are shipped to Battelle, when requested by Discovery (further information regarding associated shipping procedures is made available to study sites at the time of the request).

Further information and instructions on ADP shipping and accountability are provided in the Study Manual.

5.4 Delivery of On-Study Continuous Positive Airway Pressure

The use of nCPAP will be implemented within 90 minutes of birth. On-site study staff will be trained on the use and functionality of the nCPAP device for use during this study. The nCPAP device and training will be provided by Discovery or qualified designee.

The use of nCPAP can be preceded by intermittent positive pressure breaths using inflating pressures above the set nCPAP pressure administered manually or mechanically through a non-invasive patient interface (mask, nasal prongs) for no longer than 10 minutes after birth (eg, NeoPuff).

All local institutional policies and procedures relevant to the administration and safety surveillance of nCPAP must be followed in conjunction with study specified procedures and assessments and in accordance with good clinical practice and judgment.

During the nCPAP delivery, subjects must be closely monitored for complications related to placement of the patient interface (eg, bi-nasal prongs). Assessment must include but not be limited to evaluations for the following conditions: bleeding, apparent obstruction of the nares, occlusion of interface requiring removal and replacement, nasal irritation (erythema of nares or septum, inflammation of nares or septum).

5.4.1 Set-up of Continuous Positive Airway Pressure System

The CPAP Operator's Manual provides details on the proper set-up and operation of the nCPAP device. These procedures, in conjunction with local institutional practices, must be followed to optimize subject safety, and to ensure consistent, therapeutic pressure that minimizes resistance in the artificial and preterm infant airways.

The essential procedures to further minimize resistance during nCPAP delivery are as follows:

1. Ensure proper placement of the patient interface
Note: the device and subject interface used for nCPAP delivery during aerosol delivery must be commercially available and specifically for nCPAP delivery in neonates
2. Insert a gastric tube (open to air) after proper placement of the patient interface has been assessed.
3. Maintain the subject's neck position in a mild extension that is comfortable for the subject
4. Assess the need for nasal and oral airway suctioning and administer as needed

5.4.1.1 Initial nCPAP Settings

The initial nCPAP settings will depend on the subject's clinical condition and may be adjusted in accordance with Section 5.4.1.2; however, the following are the recommendations for initial nCPAP settings:

- $FiO_2 \geq 0.25$ (based on inclusion criteria met; refer to Section 4.2) and < 0.50 (Section 7.6)
- CPAP = 5 to 6 cm H₂O

5.4.1.2 Adjustments to nCPAP Settings

Incremental increases in nCPAP should be made by 1 cm H₂O until a maximum nCPAP of 6 cm H₂O is achieved and the following subject parameters are maintained for the duration of aerosol administration:

- SpO₂ ≥ 88 and ≤ 95%
- FiO₂ ≥ 0.25 and < 0.50 (Section 7.6)
- PCO₂ < 50 mm Hg (Section 7.1.5)
 - If a sustained nCPAP of ≥ 7 cm H₂O is necessary to maintain SpO₂ 88 to 95% or PCO₂ > 50 mm Hg, then the subject should be evaluated for clinical signs and symptoms consistent with worsening of respiratory status (Section 7.5).

5.4.1.3 Documentation of nCPAP Settings

nCPAP settings must be documented in the study eCRF at the time of initial randomization and at the following timeframes: 1, 3 (± 15 minutes), 6, 12 (± 1 hour), 18, 24, 36, and 48 hours (± 2 hours) after randomization.

5.5 Identity of Investigational Drug Product

The complete list of ingredients for the drug product is shown in [Table 5.5-1](#).

5.5.1 Formulation of Study Drug

The drug product (lucinactant) is supplied as a sterile, white, liposomal powder consisting of a 21-amino acid hydrophobic synthetic peptide, (sinapultide, KL₄ peptide), the phospholipids dipalmitoyl-phosphatidylcholine (DPPC) and palmitoyl-oleoyl-phosphatidylglycerol, sodium salt (POPG, Na), and the fatty acid palmitic acid (PA). Immediately before dosing, the lyophilized product is reconstituted with sterile water for injection at a concentration of 30 mg TPL/ml.

Table 5.5-1. Drug Description

Ingredient	Amount (ml)
Sinapultide	0.862 mg
DPPC	22.50 mg
POPG, Na	7.50 mg
PA	4.05 mg

Note: amounts reflect reconstituted product at 30 mg/ml

5.5.1.1 Aerosol characteristics

The aerosol is generated at a formulation flow rate of approximately 20 $\mu\text{L}/\text{second}$. The mass median aerodynamic diameter (MMAD) of the aerosol is below 5.0 μm . The ventilated gas that carries the aerosol to the subject has a nominal flow rate of 3 L/minute. A disposable fluid trap collects the condensed aerosol that is not transferred to the ventilation circuit (Figure 5.3-1). The specification for the aerosol temperature at the patient interface is 25°C to 38°C.

5.5.2 Packaging and Labeling

Lucinactant is supplied in 30 ml glass vials packaged in cartons with foam inserts to reduce breakage.

Lucinactant and the ADS will be appropriately labeled with the required FDA caution statements, to insure that users are aware that the product is limited by federal law to investigational use only.

